Dentistry is in need of anxiety control measures other than sedation in order to reduce risk to patients, lower the cost of treatment and increase access to dental care. The pediatric dental experience may be improved by the implementation of a therapy dog for anxiety, pain and behavior management. Our investigation will be the first to comprehensively assess physiological and psychological effects of AAT using a randomized controlled trial with a therapy dog intervention. If efficacious at anxiety, pain and behavior management, AAT will offer dental providers a non-invasive, low-risk approach to provide positive dental experiences, with the translational goal of reducing dental avoidance and its significant negative health sequelae.

EXPERIMENTAL DESIGN AND METHODS:

We have designed a cross-sectional prospective controlled trial assessing whether AAT (intervention with a therapy dog) impacts physiologic biometrics and perceptions of anxiety, pain and future expectations during a dental procedure in pediatric patients.

Screening for research participants includes searching the dental school graduate pediatric clinic schedule for potentially qualifying participants scheduled for operative or restorative dental treatment. Inclusion and exclusion criteria can be found in **Table 1**.

Table 1: Inclusion and Exclusion Criteria

Inclusion Criteria	Exclusion Criteria
Ages 7-17, male or female	Fear or allergy to dogs
Patient receiving treatment at UNC Pediatric Dental Clinic	Non-English and non-Spanish speakers
Parent and participant speak English or Spanish	Learning disability or a developmental delay
Able to comprehend and follow the requirement of the study	Medical history that complicates dental treatment
Frankl Behavioral Scale II, III, or IV	Xerostomia (dry-mouth)

This study has been approved by the UNC IRB (IRB Number: 19-1911; Title: Animal Assisted Therapy's Effects on Dental Patients)

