The research team calls to interview parents/caregivers of patients for enrollment criteria (**Table 1**). If a participant enrolls, he or she is assigned to a random weekday which determines the therapy animal's availability and will be either the active control group or the experimental AAT (dog intervention) group. The research team sets up a Go-Pro camera to film the visit and places the heart rate monitor (Shimmer or Polar device) on the patient's wrist in the pediatric clinic's consultation room. The participant is asked a standardized set of anxiety scale questionnaires: the Modified Child

Dental Anxiety Survey (MCDAS) and the Children's Fear Survey Schedule, Dental Subset (CFSS-SD). The child also rates their current pain level using Wong-Baker FACES (WBS), a numeric scale, and the visual analog scale (VAS). After the interview, the AAT intervention or control (i.e. coloring or sitting in silence) takes place for 3 minutes. The intervention group will interact with the therapy dog using a reproducible, standardized method. The handler will introduce the dog, and the participant pets the therapy dog, shakes her paw, gives her a treat, and then says goodbye in the clinic's consultation room. The control group will color a picture of a dog (active) or sit in silence (passive) for 3 minutes. C-DART database software will be used to record patient responses and guide the research visit in a structured manner. Following the intervention, the child is taken into the treatment room with the heart rate device still on his or her wrist, collecting objective physiological data. The GoPro camera will be taken into the treatment room, to provide for simultaneous video and physiological data collection. Salivary samples using salivettes will be collected at 4 timepoints during the visit, as described in **Table 1**. See **Figure 1** for treatment visit protocol.

[figure not shown]

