Table 2: Timepoints for salivary data collection

Timepoint	Description
S1	Baseline (pre-intervention, in consultation room)
S2	Post-intervention (8 minutes after intervention)
S3	8 minutes into the dental procedure
S4	8 minutes after completion of the procedure at the end of the study visit

Supplemental Aims: We will measure participants' heart rate throughout dental visit, will evaluate patients' perceptions of pain and anxiety using pre-, intra-, and post-procedural surveys and will analyze participants' behaviors using observational coding.

The Shimmer 3 GSR+ and Polar are small wearable wrist devices that measure heart rate through the wrist, with Shimmer 3 GSR+ also measuring sweat response through sensors that are fastened to the fingers. The Shimmer/Polar device will be connected to the patient during the pre-procedural interview, dog or control intervention, and procedure, continuously collecting heart rate and/or galvanic skin response (GSR) data.

Because heart rate is known to reliably increase under acute mental stress, it is widely used in medical research to evaluate stress response.³⁵ The Galvanic Skin Response (GSR) is a biomarker that quantifies the small electrical current induced by sweat which is released when the body is under stress.³⁶ The most significant psycho-activity and concentration of the epidermal sweat glands is on the sole of foot and the palm of the hand, particularly on the volar surface of the finger tips.³⁶ In a study completed by Caprara et. al in 2003, GSR was linked to increased dental anxiety in patients before undergoing a root canal treatment.³⁷

The video of the procedure as well as the heart rate data and GSR from the Shimmer device is loaded on to an external hard drive. The video will be coded with established behavioral codes using the Noldus software. The HR and GSR data are reviewed for inconsistencies using MindWare software. Both software are on a computer located in the bio-behavioral lab (BBL). The salivettes are transferred in a temperature-controlled container to the BBL where they are analyzed by ELISA for salivary alpha-amylase and salivary cortisol.

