Pre-intervention and post-intervention interviews will include the Child Fear Survey Schedule-Subset Dental (CFSS-SD), and the Modified Child Dental Anxiety Scale (MCDAS) to rate anxiety. To rate pain, the Wong-Baker FACES Scale (WBS), a numeric scale, and Visual Analog Scale (VAS) will also be used. The three pain rating scales will be repeated immediately after the injection. At the end of the procedures, the research team will repeat the CFSS-SD and the MCDAS for anxiety. They will also ask the child to rate his or her pain level again using the WBS, numeric scale, and VAS.

Pictorial representation of pain response, like The Wong-Baker FACES Scale (WBS), are preferred by children to express their level of pain regardless of age.³⁸ The Modified Child Dental Anxiety Survey (MCDAS) and the Children's Fear Survey Schedule, Dental Subset (CFSS-SD) are valid and reliable questionnaires in rating a child's anxiety in the dental setting.³⁹

STATISTICAL ANALYSIS PLAN:

To evaluate the values obtained on the various surveys, a RH Row Mean test will be utilized to compare questions that have Likert scale / ordinal responses and a chi square test will be used for categorical data. A bivariate analysis will be performed to compare the treatment outcome relative to the main exposure, which is the presence of the animal assisted therapy. The significance level will be $P < 0.05$.

Bibliography

1. Lima, D. S. M. *et al.* Does previous dental care experience make the child less anxious? An evaluation of anxiety and fear of pain. *Eur. Arch. Paediatr. Dent.* **22**, 139–143 (2021).
3. Coté, C. J. & Wilson, S. Guidelines for monitoring and management of pediatric patients before, during, and after sedation for diagnostic and therapeutic procedures. *Pediatr. Dent.* **41**, 259–260 (2019).
4. Marcus, D. A. *et al.* Animal-assisted therapy at an outpatient pain management clinic. *Pain Med.* **13**, 45–57 (2012).

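### Coded behavior would be compared by arm without the Frankl level that eligibility already requires, which gives up precision; its score and time base are also left undefined.

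*Combined protocol and SAP*

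**What the plan says.** Behavior is one of several supplemental aims: the investigators "will analyze participants' behaviors using observational coding". The Supplemental Aims text adds "The video will be coded with established behavioral codes using the Noldus software". It does not name the code set, the summary score (count, rate, share of time, worst level), the observation window or the denominator.

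Table 1 lists "Frankl Behavioral Scale II, III, or IV" among the inclusion criteria. It does not say who makes the rating or when. Frankl level does not appear again: allocation is by a weekday drawn at random, with no stated stratification, and the analysis section does not mention it.

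The Statistical Analysis Plan offers three rules. For survey items, "a RH Row Mean test will be utilized to compare questions that have Likert scale / ordinal responses". Categorical data get a chi-square test. For the rest, "A bivariate analysis will be performed to compare the treatment outcome relative to the main exposure". Only the last is general enough to cover coded behavior, and it contains no baseline term and no term for time.

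On recording, the visit description says "The research team sets up a Go-Pro camera to film the visit", before the questionnaires and the intervention. The material loaded for processing is described as "The video of the procedure as well as the heart rate data and GSR from the Shimmer device". The Figure 1 caption has video running for the whole procedure. Eligible patients are those "scheduled for operative or restorative dental treatment", and no procedure length is given.

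**The concern.** Frankl level is a rating of how a child behaves in the dental setting, so it is the natural baseline for an outcome that codes behavior in that setting. Children at levels II and IV can be expected to differ in coded behavior whichever arm they are in. An analysis that ignores this leaves the difference in the error term, although the trial needs the rating anyway to decide eligibility. What is at stake is power and the width of the confidence interval for a supplemental outcome. The primary salivary aim is not touched.

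The second, smaller matter is the time base. Because filming follows the procedure and no window is fixed, a raw count or total duration would partly measure how long the child was treated. The plan does not choose such a score, but it does not exclude one either.

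**Working it through.** The documents contain no sample size, power, effect size, standard deviation, correlation or procedure length, so there is no planned figure to reproduce. Everything below is illustrative, and the assumed inputs are marked.

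**1. Precision from Frankl level**

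*Assumed:* correlation r between Frankl level and coded behavior, 0.3 to 0.6.

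- Variance removed by adjustment = r².
  - r = 0.3: 0.09, or 9%.
  - r = 0.6: 0.36, or 36%.
- Equivalent gain in sample = 1/(1 − r²) − 1.
  - r = 0.3: 1/0.91 − 1 = 9.9%.
  - r = 0.6: 1/0.64 − 1 = 56%.

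*Further assumed:* a standardized difference of 0.5 and two-sided alpha 0.05 (the plan gives 0.05 without sidedness).

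| r | variance factor 1 − r² | n per arm for 80% power | power at 30 per arm |
|---|---|---|---|
| none | 1.00 | 63 | 49% |
| 0.3 | 0.91 | 58 | 53% |
| 0.5 | 0.75 | 48 | 61% |

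The 30 per arm is also assumed. These figures concern efficiency only; the unadjusted test keeps its error rate.

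**2. Raw total against rate, by formula**

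If total = rate × time, both lognormal and independent, the log-scale variance of the total relative to the rate is 1 + ln(1 + CV_time²)/ln(1 + CV_rate²).

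*Assumed:* CV of treatment time 0.3 to 0.5.

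- CV_rate 0.8: 1 + 0.0862/0.4947 = 1.17, and 1 + 0.2231/0.4947 = 1.45.
- CV_rate 0.4: 58% to 150% extra variance.
- CV_rate 1.5: 7% to 19% extra variance.

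The result depends heavily on an unknown rate CV. It also assumes that rate and length are unrelated, which may fail if a child who copes badly takes longer to treat.

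**3. Raw count against rate, by simulation**

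*Assumed:* 4,000 trials per setting, 30 per arm, 0.3 coded events per minute, mean procedure 40 minutes, between-child CV 0.4, overdispersed Poisson counts, rank test at 0.05.

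| Setting | Raw count rejects | Rate rejects |
|---|---|---|
| No effect, equal mean length, length CV 0 to 0.5 | 4.5% to 5.4% | 4.5% to 5.4% |
| Rate ratio 0.75, equal mean length, length CV 0.3 | 44% | 55% |
| Rate ratio 0.75, equal mean length, length CV 0.5 | 32% | 53% |
| No effect, one arm 25% longer, length CV 0 to 0.5 | 23% to 39% | 4.5% to 5.4% |
| Rate ratio 0.75, dog arm 25% longer, length CV 0 to 0.5 | 6% to 7% | 52% to 57% |

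With equal mean length the cost of a raw count is power. Bias appears only when mean length differs by arm: with no effect and 25% longer procedures, the ratio of mean counts is about 1.26 to 1.28. At 30 per arm, chance alone gives 95% limits for the arm difference in mean length of 1.96 × CV × √(2/30), that is ±15% (CV 0.3) to ±25% (CV 0.5). That chance variation is already reflected in the near-nominal first row.

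**The case against.** The strongest reply is that the plan leaves the behavior endpoint undefined rather than choosing a bad one. The codes may carry their own scoring, possibly a rate or a share of time, and an unadjusted comparison of randomized arms is valid. All of that stands.

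A reader might infer more than the documents support, in three ways.

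- *That longer treatments will look worse, or that the arm comparison is biased.* This requires a raw count or total duration, which the plan does not state. It also requires length to differ by arm, for which there is no evidence. Even unequal visit lengths are an inference from the mix of eligible treatments. If distress clusters around the injection or handpiece, a total would depend on length much less than proportionally.
- *That chance imbalance in Frankl level invalidates the comparison.* It does not; the test's error rate already allows for it.
- *That the gain is known.* The correlation has no source, and admitting only three levels tends to lower it. Rater and date are not given, so it is also unverified that a rating made before assignment exists for every child.

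Pre-intervention footage might serve as another baseline. However, the assigned weekday fixes the arm before the visit, so such footage comes after assignment, and none is named for coding.

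The reply does not remove the main point. The only analysis rule that can apply omits a baseline rating that eligibility requires.

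**Conclusion.** The point holds as a modest improvement to a supplemental analysis. Adjusting for or stratifying by the Frankl level used for eligibility is better than the unadjusted comparison and needs no extra enrollment. Its worth is about 9% to 36% of the variance if the correlation is 0.3 to 0.6, and less if the restriction to three levels weakens the correlation. The existing test is valid, so this is a matter of efficiency.

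The time-base point is secondary and conditional. A raw count or total would lose power if procedure lengths vary, and would be biased only if they vary by arm. As written, this is chiefly a missing definition. Neither gain can be sized from the documents.

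**What to change.** In the Statistical Analysis Plan, name coded behavior as an outcome and state the following.

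- **Baseline.** Compare arms stratified by, or adjusted for, Frankl level (II, III, IV) as used for eligibility. Use a rating made before the arm was assigned, never one made at the study visit, and add a missing-rating category if needed. If the row mean test named for survey items is the usual row mean scores test, it can be stratified. The plan limits it to ordinal questions, so its use here, and the scores or ranks it takes, must be written down.
- **Score.** Name the code set and score behavior as a rate or as the proportion of coded time.
- **Window.** Define it, for example from the injection or handpiece up to the S3 collection. Figure 1 puts S3 8 minutes later, and the salivette stays in for 5 minutes. State whether the 8 minutes mark placement or removal, so that coded time ends before the salivette goes in: 8 minutes in the first case, 8 − 5 = 3 in the second.

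The cost is a few sentences and one baseline variable, whose source and date need confirming. The downside is that behavior outside the window becomes descriptive. The choices should be fixed before any video is coded.

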TITLE: Evaluating effects of animal assisted therapy on anxious pediatric dental patients using objective physiologic measures and self-reports of stress

NCT NUMBER: NCT04708028

DOCUMENT DATE: March 20, 2024

TITLE: Evaluating effects of animal assisted therapy on anxious pediatric dental patients using objective physiologic measures and self-reports of stress

ABSTRACT:

A striking 50-80% of adults and 6-22% of children suffer from dental anxiety which leads to disruptive behavior during appointments and avoidance of regular dental care. Though routinely used, common pharmacological interventions (i.e. oral sedation, general anesthesia) for anxiety management carry risks of adverse effects including stress on the respiratory and cardiovascular systems, neurologic injury, and even death. Data from various healthcare settings show reductions in pain and stress indicators in patients after implementation of a therapy dog for appointments. However, few studies have explored the physiologic and subjective effects of AAT on pediatric dental patients undergoing invasive procedures. To address this gap in knowledge and explore the effectiveness of animal-assisted therapy (AAT) in pediatric dentistry, we will study the subjective and objective responses of patients undergoing operative dental procedures that include an injection.

Our central hypothesis is that children who interact with a therapy dog before their dental procedure will have significantly lower physiologic and subjective, self-reported responses to anxiety. We will test this hypothesis with the following aims: **We will measure the physiologic effects of animal assisted therapy on pediatric patients' stress levels** by analyzing salivary stress hormones (i.e. alpha-amylase and cortisol) during invasive dental procedures (primary aim). For supplemental aims, **we will measure participants' heart rate throughout the dental visit, will evaluate the patients' self-perceptions of pain and anxiety** using pre-, intra- and post-procedural validated scales to assess responses to AAT and **will analyze participants' behaviors using observational coding.** Data will guide the implementation of AAT as a non-pharmacological anxiety management tool in dentistry, with the goal of improving access to care and patient safety among anxious pediatric patients.

SPECIFIC AIMS:

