Dental anxiety is linked to avoidance behavior and an increased pain response during dental procedures.^{1,2} At this time, limited methods for non-pharmacological anxiety control exist. The burden of sedation dentistry comes with many risks and financial costs. Some serious unwanted side effects include compromise to the patient's respiratory drive, airway reflexes and airway patency, as well as the cardiovascular system.³ Sedation for anxiety control is also costly for the patient and healthcare system, with deleterious effects on access to care. **Dentistry is in need of anxiety control measures other than pharmacological sedation** to reduce the risk to patients, lower the cost of treatment and thus increase access to dental care. One promising approach is animal-assisted therapy (AAT) using a well-trained therapy dog. In medical settings, AAT has been implemented in various clinical situations and has been shown to help reduce pain and stress indicators in patients.⁴ Research into AAT as a non-pharmacological behavior management and anxiety reduction techniques in dentistry is limited as many publications are surveys⁵ with a low sample size and are not conducted in the pediatric and/or dental patient population.²

To explore the effectiveness of non-pharmacological anxiety-reduction approaches, we will study the effects of animal-assisted therapy (AAT) on pediatric patients undergoing invasive dental procedures that include an injection. The University of North Carolina has a unique opportunity to explore animal-assisted therapy because the dental school has a certified therapy dog. Our central hypothesis is that children who interact with a therapy dog before their dental procedure will have significantly lower physiologic and subjective responses to stress. We will test this hypothesis by following aims:

Primary Aim: We will measure the effects of animal assisted therapy on pediatric patients' stress levels by analyzing objective physiologic measures (salivary amylase and cortisol) during invasive dental procedures.

Supplemental Aims: We will measure participants' heart rate throughout dental visit, will evaluate patients' perceptions of pain and anxiety using pre-, intra-, and post-procedural surveys to assess the patients' subjective responses to animal-assisted therapy and will analyze participants' behaviors using observational coding.

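### Self-reported anxiety has no scheduled rating during treatment, and the interview named after the dog session has no step in the visit flow

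*Combined protocol and SAP*

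**What the plan says.** The Abstract describes self-perceptions of pain and anxiety measured "using pre-, intra- and post-procedural validated scales to assess responses to AAT". The supplemental aims, given under Specific Aims and again under Experimental Design and Methods, speak of "perceptions of pain and anxiety using pre-, intra-, and post-procedural surveys".

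The visit narrative after Table 1 puts the MCDAS and CFSS-SD before the dog or control session. Its next step for the child is: "Following the intervention, the child is taken into the treatment room". The Figure 1 legend has one survey before the procedure and one at the end of the visit that covers anxiety. Between them it lists the session, saliva samples, and the injection or handpiece.

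The interview paragraph just before the Statistical Analysis Plan is the most detailed text. It says "Pre-intervention and post-intervention interviews will include" the CFSS-SD and MCDAS for anxiety, with three scales for pain. It continues: "The three pain rating scales will be repeated immediately after the injection". For the end of the procedures it adds that "the research team will repeat the CFSS-SD and the MCDAS for anxiety", and pain is rated again as well.

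The Statistical Analysis Plan names no timepoint and no baseline adjustment for the anxiety scales. It gives a row mean test for ordinal items, a chi-square test for categorical ones, and a bivariate comparison by exposure to the dog.

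**The concern.** The central hypothesis includes subjective responses in children who meet the dog before treatment. The contact is short (three minutes in the visit narrative, two in the Figure 1 legend), and an injection and a dental procedure follow. If anxiety is next self-reported only when all of that is over, the score carries the effect of the session together with how treatment went. A supplemental aim would then have no self-report at the point where the session would be expected to act most directly. Staff following different parts of the protocol could also collect different numbers of questionnaires.

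**Working it through.** The documents give no sample size, effect size or standard deviation for these scales, so the check is a comparison of texts and a count. Anxiety self-reports by place and time:

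| Text | Before session | After session, before treatment | During treatment | End of visit |
|---|---|---|---|---|
| Abstract and both statements of the supplemental aims | promised | not distinguished | promised | promised |
| Visit narrative after Table 1 | CFSS-SD, MCDAS | no step | none | not mentioned |
| Figure 1 legend | survey | none listed | none listed | survey including anxiety |
| Interview paragraph | CFSS-SD, MCDAS | CFSS-SD, MCDAS, if *post-intervention* means this point | pain scales only | CFSS-SD, MCDAS |
| Statistical Analysis Plan | no timepoint named | no timepoint named | no timepoint named | no timepoint named |

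**Counts per child**
- Visit narrative and Figure 1 legend together: 1 before the session + 1 at the end = 2, so 2 − 1 = 1 after baseline.
- Interview paragraph, with the post-intervention interview as a separate occasion: 1 + 1 + 1 = 3, so 3 − 1 = 2 after baseline.
- Interview paragraph, with the post-intervention interview as another name for the final one: 1 + 1 = 2, so 2 − 1 = 1 after baseline.
- During the procedure: 0 in every operational text. Pain has one rating, after the injection.

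**What one later rating can show.** The difference between arms at the end of the visit is the total effect: whatever remains of the immediate effect, plus any effect that runs through how treatment went. One later rating gives one contrast, which cannot be split into these parts. A rating before treatment would supply the immediate effect directly, and the final rating would still give the total.

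**Room for the interview.** Table 2 puts S2 at 8 minutes after the intervention, and each salivette stays in place for 5 minutes. If the 8 minutes mark removal, 8 − 5 = 3 minutes are free beforehand. If they mark placement, 8 minutes are free and removal comes at 8 + 5 = 13 minutes. The text does not say which. Questions about dental fear asked before S2 could also disturb a primary-aim sample. Asking them once the salivette is out avoids both problems.

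**The case against.** The case on the other side is substantial, and most of it stands as a limit on the point.

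- **A reader might infer that the dog's effect on anxiety before and during treatment goes unmeasured.** The documents do not support that. Saliva is taken after the session (S2) and during the procedure (S3), heart rate and/or GSR run continuously, and video is coded for behaviour. Only self-report is in question, and it belongs to a supplemental aim.
- **A reader might infer that a null result on the final score would be uninterpretable.** It would not be. How the procedure went lies downstream of the session, and relief at finishing occurs in every arm. The comparison still answers a question about total effect. It just cannot show whether an early effect was absent or had faded.
- **A reader might infer that the plan definitely omits an interview after the session.** That is not established. The visit narrative is not a full schedule: it also leaves out the final survey and the pain ratings after the injection. It relies on software to structure the visit, and that structure is not in the documents. Of Figure 1, only the legend was available to this review.
- **The interview paragraph may mean the final interview when it says post-intervention.** This reading brings the texts into agreement, but it confirms that no anxiety self-report falls between the session and the end of treatment.
- **The aims may use the word for during-procedure ratings collectively, with pain satisfying it.** That is possible, but the aims pair pain and anxiety without distinction, so they should state it.

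**Conclusion.** The point holds for self-reported anxiety only, and its two parts differ in certainty. The missing rating during the procedure is definite: it is promised in three places and scheduled in none. The rating between the session and treatment is an unresolved ambiguity, worth one later anxiety self-report per child or two. If staff follow the visit narrative and the Figure 1 legend, the trial can compare arms on total effect at the end of the visit but cannot isolate the immediate effect on self-reported anxiety. Calling that comparison valid assumes that allocation to arms is sound, which is a separate matter. The primary salivary aim and the other physiologic and behavioural measures are untouched. This is a cheap improvement and not a threat to the trial's main result.

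**What to change.** 1. Reconcile the visit narrative, the Figure 1 legend and the interview paragraph. Define the post-intervention interview, with at least the MCDAS, as one fixed point after the dog or control session and before treatment. It should be the same for the dog, coloring and silence conditions, and preferably come once the S2 salivette has been removed. A single table of scales by timepoint would do this.
2. In the Statistical Analysis Plan, compare arms on that score and on the end-of-visit score, each adjusted for the pre-intervention score, in place of the unadjusted bivariate test. State that the first addresses the immediate effect and the second the total effect. The baseline score is already collected. The gain in precision depends on its correlation with the later scores, which the documents do not give.
3. Amend the aims to say that self-report during the procedure covers pain only.

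The cost is protocol and analysis-plan wording, a few minutes of the visit, and one more short questionnaire per child given by the same staff. The extra questions could in principle influence later measures such as S3, but they would be asked identically in all arms.

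### The survey analysis defines no questionnaire totals, gives the pre-intervention scores no role, and names no lead among at least eight scale-level tests at an unadjusted 5%

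*Combined protocol and SAP*

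**What the plan says.** The Statistical Analysis Plan is one short paragraph. For survey values it names a row mean test "to compare questions that have Likert scale / ordinal responses" and states that "a chi square test will be used for categorical data". It then adds: "A bivariate analysis will be performed to compare the treatment outcome relative to the main exposure", the exposure being the therapy dog. The outcome in that sentence is not defined. One significance level, P < 0.05, covers everything. The paragraph contains no total or summary score, lead scale, lead time, baseline covariate or multiplicity rule.

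The survey measures are described in Experimental Design and Methods. MCDAS and CFSS-SD rate anxiety, and the protocol calls both questionnaires valid and reliable. For pain: "To rate pain, the Wong-Baker FACES Scale (WBS), a numeric scale, and Visual Analog Scale (VAS) will also be used". All five instruments are completed before the 3-minute intervention. Then "The three pain rating scales will be repeated immediately after the injection", and all five instruments are given again at the end of the procedure. The same section also mentions a post-intervention interview, without saying whether it is separate from the one at the end.

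The surveys belong to the supplemental aims, and the primary aim is salivary amylase and cortisol. The central hypothesis nevertheless covers subjective as well as physiologic responses.

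**The concern.** Three gaps come together.

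- **Unit of analysis.** The validity that the protocol relies on is that of the questionnaires, but the only unit named for the ordinal test is the question.
- **Baseline.** A bivariate comparison relates one outcome to one exposure. The trial collects a pre-intervention score on every scale, and the plan does not say how any of them will be used.
- **Selection.** Three scales rate the same pain at two or more post-baseline times, alongside two anxiety questionnaires, and all results have equal standing at 5%.

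At stake is the subjective half of the central hypothesis. The plan does not say which result would confirm or refute it, so a reader of the report could not tell a planned finding from a selected one.

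**Working it through.** The documents give no sample size, power, SD, effect size or item count, so there is no figure of the plan's own to reproduce beyond the 5% level. Tests are taken as two-sided, because sidedness is not stated.

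**1. Number of scale-level tests** (from Experimental Design and Methods)
- Interview after the procedure only: 3 pain scales × 2 times + 2 anxiety questionnaires × 1 time = 6 + 2 = 8.
- Separate post-intervention interview as well: 3 × 3 + 2 × 2 = 9 + 4 = 13.

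**2. Chance of at least one false positive, each test at 5%**

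For independent tests it is 1 − 0.95^k. For correlated tests it comes from simulation of equally correlated normal test statistics (200,000 draws). The correlations are assumptions.

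| Tests | Independent | Correlation 0.5 | Correlation 0.8 |
|---|---|---|---|
| 3 (pain, one time) | 14.3% | 12.6% | 9.9% |
| 6 (pain, two times) | 26.5% | 20.7% | 13.9% |
| 8 (all scales) | 33.7% | 25.1% | 15.8% |

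With 13 tests the independent figure is 1 − 0.95^13 = 48.7%. At correlation 0.8 it lies between the simulated values for 10 tests (17.5%) and 15 tests (20.2%).

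If single questions were tested, the figure would depend on an item count that the documents do not give. For an assumed 10 questions it is 40.1%, 28.6% and 17.5% across the same three columns. For an assumed 20 it is 64.2%, 42.0% and 22.3%.

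**3. Baseline adjustment**

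The share of outcome variance removed is ρ², where ρ is the correlation between the pre-intervention and later score. For an assumed ρ of 0.5 it is 0.25, and for 0.7 it is 0.49.

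**4. Total against single question**

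If all m questions share the same standardised effect and have common correlation r, the total has √(m / (1 + (m − 1)r)) times the standardised effect of one question. For an assumed m = 10:
- r = 0.3: √(10 / 3.7) = 1.64
- r = 0.5: √(10 / 5.5) = 1.35

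An illustration with every input assumed (10 questions, r = 0.5, 50 per arm, effect 0.4 SD per question) gives power of 77% for the total and 52% for one question. The chance that at least one of the ten unadjusted question tests is significant is 92%.

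The ordering can reverse. If only one of ten questions moves, by 0.6 SD, that question has 85% power. The total's effect is then 0.6 / √(10 + 90 × 0.5) = 0.6 / 7.42 = 0.08 SD, with 6% power.

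**5. Two lead tests**

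At 5% each, 1 − 0.95² = 9.75% if independent. At 2.5% each, 1 − 0.975² = 4.9%.

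**The case against.** The plan does not reject totals; it is silent on them. The post-procedure survey also asks about experience and future expectations (Figure 1 caption), where comparing single questions is natural, and the word may refer to those. A reader might infer that the SAP has chosen item-level analysis of MCDAS and CFSS-SD. The documents show only that totals are never defined. The point about totals also does not reach the three pain scales, which are read here as single ratings.

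A reader might also infer that question-level testing loses power. Step 4 shows that this holds per test when the effect is shared across questions, and fails when it is concentrated in one.

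Nor do the figures support saying that a false positive is likely at scale level: with 8 tests the range is 16% to 34%, and overlap between the scales pulls it towards the lower end.

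Finally, an unadjusted comparison is valid under randomisation, so baseline adjustment is a gain in precision and not the repair of a bias. The outcome is undefined, so a change score is not excluded, but none is mentioned. The surveys are supplemental, and labelling them exploratory would largely answer the multiplicity point.

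All of this stands. It narrows the concern without removing it: the plan still does not define the variables, use the baseline scores, name a lead or attach an exploratory label.

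**Conclusion.** The point holds as a gap in specification for the supplemental survey outcomes. With at least 8 scale-level tests at an unadjusted 5%, the chance of at least one false positive is about 16% to 34% for 8 tests, given two-sided tests with common correlation between 0.8 and 0. It is higher if the post-intervention interview is separate and there are 13. Precision is also left unused: 25% to 49% of outcome variance at an assumed baseline correlation of 0.5 to 0.7.

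Any power advantage of totals over single questions is conditional on a shared effect, and cannot be sized for this trial without a sample size, SD or item count. A reader might extend the false-positive figures to the primary aim. They do not apply there, because salivary amylase and cortisol are separate outcomes whose error rate these survey tests do not change.

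**What to change.** Amend the Statistical Analysis Plan before any survey outcome is compared by group:

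- Analyse the MCDAS and CFSS-SD total scores at the end of the procedure by ANCOVA, adjusted for the pre-intervention total.
- Analyse each pain rating adjusted for its pre-intervention value, with an ordinal or rank-based model if the distribution calls for it.
- Name one lead anxiety total. The choice is the sponsor's, since the protocol credits both questionnaires with validity.
- Name one lead pain scale and time. WBS has support in the protocol's own remark that children prefer pictorial scales. The time must also exist for every child: the Figure 1 caption allows handpiece insertion as an alternative to an injection, while the Abstract and Specific Aims describe procedures that include an injection. Those passages need to be reconciled.
- Either test the two leads within one 5%, split (for example 2.5% each) or in a fixed order, or label all survey tests exploratory.
- Report every other scale, time and single question descriptively with confidence intervals.
- State whether the post-intervention interview is separate from the end-of-procedure one.

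The cost is SAP wording; no new data are needed. Fewer survey results can be called significant, and an effect confined to one question would be diluted in the total, which is a reason to keep the single-question results in the descriptive tables.
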